6.2.1.1 Adverse Events of Interest (AEI) and Other Important AEs

Summaries for treatment-emergent AEIs events will be provided by PT for each AEI category.

- Skin-related events
- Infection events
- Malignancy events

Creatine kinase (CK) elevation for CK elevation > 2.5 upper limit of normal will be summarized as CTCAE grade 2 or higher in the clinical laboratory summaries.

Additional information collected for some events as part of the clinical safety program and adjudicated events will also be summarized.

6.2.1.2 Serious Adverse Events

Summaries for treatment-emergent SAEs will be provided for the following:

- Treatment-emergent SAEs by SOC and PT

6.2.1.3 Adverse Events Leading to Discontinuation of Study Treatment or Study Treatment Interruption

Summaries for TEAEs leading to discontinuation of study treatment will be provided for the following:

- TEAEs by SOC and PT

Summaries for TEAEs leading to study treatment interruption will be provided for the following:

- TEAEs by SOC and PT

6.2.2 Deaths

All adverse events with an outcome of death will be listed.

6.2.3 Clinical Laboratory Data

Laboratory parameters will be summarized using the International System (SI) of Units. Data will be summarized by time point, as applicable. The following summaries will be provided for each parameter:

- Absolute, change from baseline values for continuous parameters
- Number and percentage of subjects for the following:
 - Maximum postbaseline CTCAE grade for each applicable laboratory parameter

Sponsor: Bristol-Myers Squibb
Protocol no: IM011065

- Shifts from baseline based on maximum postbaseline CTCAE grade
- Drug-induced Liver Injury (DILI) and Hy's Law summaries

6.2.4 Vital Signs and Physical Findings

Vital signs, including weight, will be summarized by time point, as applicable. The following summaries will be provided for each parameter:

- Absolute and change from baseline values
- Number and percentage of subjects for the following:
 - Marked abnormality for each abnormality category as defined in [Section 4.2](#)

6.2.5 ECGs

ECG parameters will be summarized by time point, as applicable. The following summaries will be provided for each parameter:

- Absolute, change from baseline values and change from baseline in maximum post-baseline value for continuous parameters
- Number and percentage of subjects for the following:
 - Marked abnormality for each abnormality category as defined in Section 4.2

6.2.6 Other Safety Data

6.2.6.1 PHQ-8

PHQ-8 total score will be summarized by time point, as applicable. The following summaries will be provided:

- Absolute and change from baseline values
- Number and percentage of subjects:
 - Shifts from none, mild, moderate, moderately severe and severe scores at baseline and at each time point

6.2.6.2 eC-SSRS

Suicidal ideation and behavior individual item responses will be summarized by time point, as applicable. The following summaries will be provided:

- Number and percentage of subjects with positive responses on suicidal ideation and/or suicidal behavior questions for each question and overall all questions within suicidal ideation and suicidal behavior
- Shifts from baseline based on maximum postbaseline response
- Worst postbaseline value for suicidal ideation and behavior

6.3 General Methodology

The following standards/ methods will be used:

- Statistical package(s) planned to be used
 - All analyses will use SAS version 9.4 or higher.

Sponsor: Bristol-Myers Squibb
Protocol no: IM011065

- Standard summary statistics for continuous and categorical variables:
 - Unless otherwise noted, categorical variables will be summarized using counts and percentages. Percentages will be rounded to one decimal place, except 100% will be displayed without any decimal places and percentages will not be displayed for zero counts.
 - Continuous variables will be summarized using the number of observations (n), mean, standard deviation (SD), median, minimum and maximum. The median, minimum and maximum values will be displayed to the same level of precision as the raw data, the mean to a further decimal place and the SD to two additional decimal places.
 - Variables will be summarized by period, treatment group, and time point, as applicable.

6.3.1 Subject Populations and Disposition

The number of subjects enrolled/screened and the number and percentage of subjects randomized, treated, and in each analysis population will be presented. The number and percentage of subjects randomized in each country and site will be presented.

Additionally, the following summaries will be provided for the FAS by treatment group and overall:

- Number and percentage of subjects who completed 16 weeks of treatment
- Number and percentage of subjects who discontinued treatment prior to Week 16 and reason for treatment discontinuation
- Number and percentages of subjects who completed 52 weeks of treatment, who discontinued treatment prior to Week 52 and post Week 16, and who discontinued treatment at any time and reason for treatment discontinuation. Denominator will be the number of subjects in the FAS.

6.3.2 Demographic and Baseline Characteristics

Demographic and baseline characteristics will be summarized by treatment group for the FAS. Demographic characteristics include the following:

- Sex
- Race
- Ethnicity
- Age (in years, at time of signing informed consent) and age category (<65 vs ≥65)
- Weight (in kg, at baseline) and weight category (<90 kg vs ≥90 kg)
- Body mass index (BMI in kg/m², at baseline)
- Country (Mainland China, Taiwan, South Korea)
- Prior biologic use for psoriasis, psoriatic arthritis and other inflammatory diseases only (yes, no)
- Reason for discontinuation of prior biologic use

Sponsor: Bristol-Myers Squibb

Protocol no: IM011065

- Prior systemic treatment use (yes/no)
- Prior phototherapy use (yes/no)
- Stratification factors obtained from IRT: country (mainland China, non-Mainland China) and prior biologic use
- Stratification factors obtained from database: country (mainland China, non-Mainland China) and prior biologic use
- sPGA (3, 4)
- PASI score (≤ 20 , > 20)
- BSA involvement (10-20, > 20)
- Duration of disease (< 10 y, ≥ 10 y)
- Age at disease onset (< 18 , 18-39, ≥ 40)

Additional demographics or baseline data may be added to summary tables.

General medical history and medical history related to psoriasis will be coded using the Medical Dictionary for Regulatory Activities (MedDRA 23.1 or later). General medical history data will be summarized for each SOC and PT by treatment group and overall for the FAS. Separate tables will be provided for psoriasis medical history.

6.3.3 Prior and Concomitant Medications

Prior and concomitant medications will be coded according to World Health Organization-Drug Dictionary WHO-DD (version at the time of DBL) and will be summarized by Anatomic Therapeutic Classification (ATC) and preferred term (PT) by treatment group for the As-treated population. The number and percentage of subjects using at least one medication and each medication will be displayed by treatment group. Subjects taking more than one medication within the same ATC or PT will be counted once.

Prior medications are defined as medications that started prior to first study treatment, but no longer being taken at the time of the study. i.e. start and stop prior to the first study treatment.

Concomitant medications are defined as medications that were ongoing at the time of first dose of study treatment, or started on or after the first dose of study treatment but before the last dose of study treatment.

Post study medications are defined as medications that started after the last dose of study treatment.

Summaries will be provided for prior medications as well concomitant medications.

Medication dates will be imputed according to algorithms detailed in [Section 8.0](#). The imputed dates will be used to assess whether medications should be included in the summaries as prior or concomitant, however the original, partial dates will be included in data listings.

Sponsor: Bristol-Myers Squibb
Protocol no: IM011065

6.3.3.1 Psoriasis, Psoriatic Arthritis and Other Inflammatory Disease Related Systemic Medications

Prior medications that started and stopped prior to first treatment start date for systemic biologic and non-biologic medications will be summarized as described above for the number and percentage of subjects using each reported medication.

6.3.4 Exposure

6.3.4.1 Duration of Treatment

Duration by Group

Overall duration of each treatment, in days, will be calculated for each subject in each treatment group. Subjects are dispensed study treatment at each visit, starting with Day 1 (Week 0) and at each subsequent visit. The date of first dose of study treatment is the Week 0 [redacted] dosing date and is recorded on the eCRF. If this date is missing, then the earliest drug dispensation date will be used. The last dose date is recorded on the end of treatment page in the eCRF. If this date is missing, then the latest date from the [redacted] page or drug accountability return date will be used.

Duration of treatment will be summarized descriptively by treatment group.

BMS-986165:

Subjects randomized to BMS-986165 will have their duration of treatment derived as:

- Date of last dose – date of first dose +1

Placebo:

For subjects randomized to placebo, duration is defined as:

- Placebo = Date of last dose of placebo – date of first dose +1
- BMS-986165 = Date of last dose of BMS-986165 – date of first dose of BMS-986165 +1

Duration by Period

Overall duration (in days) of each treatment received within each study period will be calculated. Duration within each period is defined for each treatment group as:

$$\text{Last dose date} - \text{first dose date} + 1$$

6.3.4.2 Summary of Dosing

The number of doses taken for each subject for each period will be determined using the eCRF drug accountability data and is defined as:

$$\text{Doses Taken} = (\text{number of tablets dispensed} - \text{number of tablets returned})$$

The number of doses taken will be summarized descriptively by treatment group within each period and overall.

6.3.4.3 Compliance

Treatment compliance will be determined from data captured on the Drug Accountability eCRF.

[figure not shown]
$$\text{Number of expected doses} = (\text{date of next visit} - \text{date of current visit})$$

Sponsor: Bristol-Myers Squibb
Protocol no: IM011065

Treatment compliance will be derived for each period. Compliance is defined as:

$$\left(\frac{\text{Number of doses taken}}{\text{Number of expected doses}} \right) \times 100$$

Period compliance will be calculated by summing over all visits within the period using descriptive statistics by treatment group. The number and percentage of subjects with <75%, 75% to 100%, and >100% compliance will be provided by treatment group for each period. If a subject does not return the container, then this dispensation event will be excluded in the calculation for the total number of doses taken, total number of expected doses, and total compliance.

6.5.2 Impact on Safety Endpoints

No modifications will be made for the presentations of safety data due to COVID-19. There will not be additional safety data handling considerations for missing data or treatment interruptions due to COVID-19.

6.6 Country Specific Analyses

Country or region specific analyses may take place to support submissions to regional health authorities. In general these would consist of repeating a subset of the analyses described in this SAP for subjects from a specific country, which would potentially be used for evaluation of consistency between the country and the overall population.

Unless otherwise noted, the same analysis methods will be used as for the global population. Also, unless otherwise noted, no formal hypothesis testing will be performed and descriptive summary statistics and estimates will be provided for evaluation of consistency of the population. No adjustment for multiplicity will be made. Stratification factors may or may not be used in analyses as appropriate, taking into account the size of the population.

Country specific analysis will be performed for the Greater China subgroup. This population contains subjects that are Chinese by race and enrolled at sites within mainland China and National Medical Products Administration certified sites within Taiwan.

7.0 Sequence of Planned Analyses

7.1 Interim Analyses

No interim analysis is planned for this study.

7.2 Final Analyses and Reporting

An unblinded analysis of the data collected up to Week 16 will be conducted once all randomized subjects have either completed the placebo-controlled treatment period (ie, through Week 16) or have discontinued prior to Week 16. A final database lock and analysis will occur after all subjects complete Week 52 or discontinue prior to Week 52. See [Section 2.4](#) for detailed information about unblinding and analysis and reporting at Week 16 and Week 52.

All final, planned analyses identified in this statistical analysis plan will be performed only after the last subject has completed the study and the database has been locked. The randomization codes for all subjects will remain blinded until after the database has been locked.

8.0 Conventions

8.1 General Definitions

The following data definitions and handling conventions will be used for general analysis:

Sponsor: Bristol-Myers Squibb
Protocol no: IM011065

Term	Definition
Study Day	
For dates prior to the first dose date, assessment date – first dose date
 
For dates on or after the first dose date, assessment date – first dose date + 1 day

Baseline	
Unless otherwise stated, Baseline is defined as the last measurement at the randomization visit (Week 0). If the measurement on Day 1 is missing, then a prior measurement during the screening period may be used as baseline. Baseline assessments must be performed per protocol and standard of care assessments may not be used for baseline.
 
Baseline for each PSSD question will be calculated as the average value over the 7 days prior to the randomization visit. In the event of missing values in the 7 days prior to the randomization visit, daily scores from at least 4 days out of the 7 days can be used to calculate the average score. If > 3 daily scores in the last 7 days are missing for a particular question, then the baseline value for that question will be missing. If any questions are missing baseline after using the described rule, then the baseline value for the subscore using that question and the baseline value for the total score will be missing.

Change from Baseline	Change from baseline is defined as (value at post-baseline visit – value at baseline).
Change from baseline to the maximum post-baseline value or change from baseline to the worst post-baseline value	The maximum/worst post-baseline value is defined as highest/worst observed post-baseline value. The change from baseline is calculated using this maximum/worst value - baseline value.
Concomitant and Prior Medication	
Prior medications are defined as medications that started prior to first study treatment, but no longer being taken at the time of the study. i.e. start and stop prior to the first study treatment.
 
Concomitant medications are defined as any medications ongoing at the start of study treatment or with a start date on or after the first dose date and prior to the last dose date.
 
Post study medications are defined as medications that started after the last dose of study treatment.

End of Study (EOS) Date	The EOS date is the date recorded on the eCRF that a randomized subject either discontinued or completed the study. If the subject is lost to follow-up, the EOS date will be the date of the last visit assessment obtained.
Exposure-adjusted incidence rate (EAIR)	EAIR = $100 * 365.25 * (\text{total number of subjects with the AE}) / \text{total exposure time for the selected AE}$ under each

Sponsor: Bristol-Myers Squibb
Protocol no: IM011065

	
treatment that a subject is exposed. Where total exposure time for each AE within a treatment is calculated as follows:
 
• If a subject has at least 1 treatment emergent event while on a particular treatment, then the exposure time for that subject and AE on that treatment is:
◦ First AE onset date – treatment start date (of that particular treatment) +1• If a subject does not have an event, exposure time for that AE is:
◦ Treatment stop date (of that particular treatment) – Treatment start date (of that particular treatment) + 1 + 30 days (if subject discontinued or subject completed but is not rolling into IM011075 study)◦ Treatment stop date (of that particular treatment) – Treatment start date (of that particular treatment) + 1 (if subject completed and is rolling into IM011075 study) 
Total exposure time = sum of exposure time for each AE within a treatment

First Dose Date – Study	The date a subject received their first dose on Day 1 as recorded in the eCRF Week 0 [redacted] dosing date or the earliest drug dispensation date.
Last Dose Date – Study	The date of last recorded dose on the End of Treatment eCRF for a randomized subject. If this date is missing, the latest date from the [redacted] exposure page or drug accountability return date will be used.
First Dose Date – Period	The date a subject received their first dose as recorded in the eCRF Week 0 [redacted] dosing date or the earliest drug dispensation date for Treatment Period 1 and the earliest drug dispensation date for Treatment Period 2.
Last Dose Date – Period	The date of the last visit in the periods – 1. If a subject prematurely discontinues study treatment within a period, the date of last recorded dose on the eCRF will be used as the last dose date for the period.
Percent Change from Baseline	Percent change from baseline is defined as $([\text{value at post-baseline visit} - \text{value at baseline}]/\text{value at baseline}) \times 100$. If the baseline value is 0 and the post-baseline value is also 0, then the percent change from baseline is set to 0. If the baseline value is 0 and the post-baseline is >0, then the percent change from baseline value will be missing.

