6.0 Statistical Analyses

Descriptive summaries and analyses outlined in [Appendix 1](#) will be presented for data captured throughout the study using the following treatment groups.

For the comparison of endpoints collected during the first 16 weeks of treatment, summaries will be provided for the following treatment groups:

- BMS-986165 6 mg QD
- Placebo

After Week 16, data will be presented for the following treatments:

- BMS-986165 6 mg QD (starting from Week 16 through Week 52)
- Subjects who switched from placebo to BMS-986165 6 mg QD (including Week 16 through Week 52)
- All BMS-986165 6 mg QD (all subjects exposed to BMS-986165 6 mg QD; includes subjects on placebo that switched to BMS-986165 6 mg QD)

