6.2 Safety

Summaries of safety data will be presented by period and treatment group, as applicable, for the As-treated population.

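### Safety baseline stays at Week 0 for placebo subjects who switch at Week 16, so changes that arose on placebo enter the drug-exposure tables, and the SAP leaves open which switch-visit and All-BMS values count

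*SAP*

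**What the plan says.** **Baseline.** SAP 8.1, subject to exceptions stated elsewhere: "Baseline is defined as the last measurement at the randomization visit (Week 0"; a screening value may stand in if Day 1 is missing. The only special rule is for the PSSD. Nothing in the available text sets another baseline for subjects who move from placebo to BMS-986165.

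**Worst value.** SAP 8.1: "The maximum/worst post-baseline value is defined as highest/worst observed post-baseline value". The change to it is taken from the same baseline. The definition itself carries no treatment or period limit.

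**Columns after Week 16.** SAP 6.0 lists three. The arm that stays on BMS-986165 is shown from Week 16 to Week 52. The switch column is "Subjects who switched from placebo to BMS-986165 6 mg QD (including Week 16 through Week 52". The All-BMS column is "all subjects exposed to BMS-986165 6 mg QD; includes subjects on placebo that switched to BMS-986165 6 mg QD", with no time limit. Protocol 9.5 lists the same three columns for safety.

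**Period rules.** SAP 6.2: "Summaries of safety data will be presented by period and treatment group, as applicable, for the As-treated population". SAP 6.3: "Variables will be summarized by period, treatment group, and time point, as applicable". SAP 8.4 ends Period 1 on the Week 16 visit date and starts Period 2 the day after. SAP 8.5 places the Week 16 window in Period 1.

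**Timing at Week 16.** The notes to the Protocol 1.3 schedule put the visit-day dose after the blood draws, and both permitted orders of assessment place safety assessments before those draws.

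**The concern.** For a subject who stays on BMS-986165, Week 0 is the last point before exposure. For a switched subject it is not: 16 weeks on placebo lie in between. Several planned safety outputs are built on change from baseline: the marked vital-sign categories and QTcF change bands (SAP 4.2), laboratory shifts by maximum CTCAE grade (6.2.3), and PHQ-8 shifts (6.2.6.1). In the switch and All-BMS columns these mix what happened on placebo with what happened on drug. Restricting the post-baseline values to Period 2 does not help, because it leaves the baseline where it was.

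Two narrower gaps sit beside this. SAP 6.0 brings Week 16 into the switch column while 8.4 keeps that visit date out of Period 2, although Week 16 safety values precede the first active dose. And the All-BMS column does not say which values of switched subjects feed maximum or worst-value tables.

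At stake is how far the 52-week laboratory, vital-sign, ECG and PHQ-8 tables can be read as describing time on drug.

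**Working it through.** The documents give no figure for this point, so there is none to reproduce. The check sets the rules side by side and sizes them.

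**1. Who is affected.** Protocol 4.2: about 219 subjects, 2:1. Placebo 219/3 = 73; BMS-986165 146. With full enrolment and no dropout, switched subjects are 73/219 = 33.3% of All-BMS.

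**2. What the Week 0 baseline does.** For a switched subject,

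change from Week 0 = change on placebo (P) + change on drug (D).

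One marked heart-rate category in SAP 4.2 needs a value above 100 and a change above 30. The change part is met when P + D > 30. If P is positive it can be met with D ≤ 30, and a change partly due to placebo time is shown on drug. If P is negative it can fail with D > 30, and a drug-phase rise is missed. The error runs in either direction.

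**3. Size of the upward part (assumed rates).** Let r be the share of placebo subjects who develop a change by Week 16 and s the share of those that persist. Affected subjects = 73 × r × s.
- r = 2%, s = 25%: 73 × 0.02 × 0.25 = 0.4 subjects; 0.4/219 = 0.2 points in All-BMS.
- r = 5%, s = 50%: 1.8 subjects; 0.8 points.
- r = 10%, s = 100%: 7.3 subjects; 3.3 points.

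**4. Which placebo-phase values reach the switch column.** SAP 6.2 and 6.3 summarise by period, 8.4 starts Period 2 after the Week 16 visit, and 6.0 heads the column from Week 16. Read together, Weeks 1-12 stay out. Only the Week 16 value is in dispute: in under 6.0, out under 8.4 and 8.5. In a by-visit table this is harmless, since it shows the pre-switch level. In a maximum-value table it adds one on-placebo reading, and a high placebo reading can hide a later rise on drug.

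The schedule has chemistry at 6 post-baseline visits up to Week 16 (Weeks 1, 2, 4, 8, 12, 16) and 9 after it (Weeks 20 to 52). With an assumed per-visit chance q of an abnormal value, independent between visits and unrelated to drug, P(at least one in k visits) = 1 − (1 − q)^k:

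| q | Switch column, on drug only (k = 9) | plus Week 16 (k = 10) | all post-baseline visits (k = 15) |
|---|---|---|---|
| 0.5% | 4.4% | 4.9% | 7.2% |
| 1% | 8.6% | 9.6% | 14.0% |
| 2% | 16.6% | 18.3% | 26.1% |
| 5% | 37.0% | 40.1% | 53.7% |

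The Week 16 conflict is worth about 0.5 to 3 points. The last column would apply only with no period limit at all, which is not the plain reading for the switch column.

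**5. The All-BMS column.** Drug exposure through Week 52 is 146 × 52 + 73 × 36 = 10,220 person-weeks.
- If the column takes only data after Week 16, it loses 146 × 16 = 2,336 person-weeks on drug, 22.9% of 10,220.
- If it takes all post-baseline data, it gains 73 × 16 = 1,168 placebo person-weeks, 10.3% of 11,388.
- The natural meaning, data after each subject's first BMS-986165 dose, is not written down.

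Under the model in step 4, with the BMS-986165 arm counted over Weeks 1-52, All-BMS is 12.2% on drug only and 14.0% with all values at q = 1%; 6.3% and 7.2% at q = 0.5%; 48.1% and 53.7% at q = 5%.

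**The case against.** The strongest reply is that the SAP already limits safety summaries by period and treatment group, so placebo-phase data stay in the placebo-phase tables. For the switch column and Weeks 1-12 this is right. A reader who takes the worst-value definition alone might infer that every placebo-phase result is charged to the drug; SAP 6.0, 6.2, 6.3 and 8.4 together do not support that. What remains is the Week 16 conflict and the All-BMS column, where the words as applicable do not settle the matter. None of this answers the baseline point, since a period limit on later values does not move the baseline.

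A reader might also infer that creatine kinase is exposed in particular, because its elevation "will be summarized as CTCAE grade 2 or higher in the clinical laboratory summaries". The count at grade 2 or higher uses the absolute grade, so the choice of baseline does not alter it. Clinically significant laboratory results are also recorded as adverse events (Protocol 8.2.7) and assigned to a period by onset. The documents do not make creatine kinase a special case.

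Nor does the plan bias only against BMS-986165: step 2 shows that it can go either way. The eC-SSRS shifts share the baseline rule, but Protocol 7.1 ends study treatment for subjects who report suicidal ideation or behavior after randomization, so few such subjects should reach the switch.

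Finally, laboratory, vital-sign, ECG and PHQ-8 data are also summarised by time point, so the Week 16 level can be seen. That helps with means by visit, but not with shift and threshold tables, which report each subject against Week 0.

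**Conclusion.** The point holds in this form. The SAP states a Week 0 baseline for everyone, and for up to 73 switched subjects that is 16 weeks before first BMS-986165. Their change and shift results in the switch and All-BMS columns combine placebo time with drug time, in either direction. Under the assumed rates in step 3 the upward part is 0.4 to 7.3 subjects, or 0.2 to 3.3 points in All-BMS. The Week 16 value and the All-BMS data rule are unresolved wording, not a stated rule that counts all placebo data as drug data.

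The counts assume full enrolment, no dropout and every placebo subject switching, so they are upper limits; the rates r, s and q are not in the documents. Adverse-event tables (assigned by onset within a period), exposure-adjusted incidence rates (based on the dates of the particular treatment), the randomized Week 0-16 comparison and the coprimary analyses are unaffected. This is a cheap improvement to descriptive safety tables.

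**What to change.** For the switch and All-BMS safety summaries:

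- (a) Define baseline as the last value on or before the first BMS-986165 dose: the Week 16 visit for switched subjects, Week 0 for the arm randomized to BMS-986165.
- (b) Limit maximum and worst post-baseline values to those after that dose, and state that this rule governs the All-BMS column.
- (c) Reconcile the switch-column heading in SAP 6.0 with the Period 2 start in 8.4, so that the Week 16 value has one role.

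Keep Week 0 as baseline for efficacy and for the placebo-controlled period.

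The cost is one definition, one derived baseline flag and a footnote. Week 16 chemistry, vital signs, ECG, PHQ-8 and eC-SSRS are already in the schedule, and SAP 1.0 provides for an updated SAP before final database lock. The drawback is that readers must keep two baseline definitions apart, so each table needs to name the one it uses.

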9.5 Safety Analyses

Safety data will be analyzed for AEs, SAEs, laboratory analytes, vital signs, ECGs, and suicidality and depression. Safety will be summarized using the As-treated population. Categorical data will be summarized as frequency counts and percentages. Continuous data will be summarized using n, mean, standard deviation, median, minimum, and maximum unless otherwise specified.

During the first 16 weeks of treatment data will be presented for the following treatments:

- BMS-986165 6 mg QD
- Placebo

After Week 16 data will be presented for the following treatments:

- BMS-986165 6 mg QD
- Placebo→BMS-986165 6 mg QD (starting from Week 16 through Week 52)
- All BMS-986165 6 mg QD (all subjects exposed to BMS-986165 6 mg QD; includes subjects on placebo that switched to BMS-986165 6 mg QD)

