6.2.1 Adverse Events

Adverse events will be presented for the number and percentage of subjects and the number of events. Treatment-emergent will be provided in listings. Summary tables will be reported in decreasing frequency based on the total column. Counting for frequency analysis will be by subject and not by AEs, and subjects are only counted once for recurring AEs within each system organ class (SOC) or preferred term (PT); however, the number of total AEs per subject, including multiple occurrences of individual AEs, will also be presented. For summaries of severity, AEs will be reported only at their maximum severity in each subject. Subjects with multiple AEs within a particular SOC or PT will be counted under the category of their most severe event within that SOC or PT.

AE (including deaths) dates will be imputed according to algorithms detailed in [Section 8.0](#). The imputed date of AE onset will be used to assess whether AEs should be considered as treatment-emergent and included in the safety summaries. The original, partial dates will be included in data listings. No imputation will be performed on missing AE seriousness, severity, or relationship; they will be reported as missing.

AEs will be included in a period if the start date of the AE is after the first dispensation date within a period.

An overall summary for the following categories will be presented:

- Deaths
- SAEs
- Related SAEs
- AEs
- Related AEs
- Discontinued treatment due to AEs

The following summaries will also be provided for the following:

- TEAEs by SOC and PT
- Treatment-related TEAEs by SOC and PT

Sponsor: Bristol-Myers Squibb

Protocol no: IM011065

- TEAEs by PT reported in $\geq 5\%$ of subjects
- TEAEs by PT reported in $\geq 1\%$ of subjects
- Treatment-related TEAEs by PT reported in $\geq 5\%$ of subjects
- TEAEs categorized by severity by SOC and PT
- Exposure-adjusted incidence rate (EAIR) for TEAEs by SOC and PT – EAIR is defined in [Section 8.1](#) of the SAP.

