8.4 Study Periods

Period 1 = Week 0 to Week 16 visit date

Period 2 = Week 16 visit date +1 to Week 52 visit date

Follow-up = 4 week follow-up period

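### The SAP's exposure-adjusted incidence rate has no rule for placebo that ends at the Week 16 switch, so a placebo rate run at the final lock can count 30 days on BMS-986165 as placebo time

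*SAP*

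**What the plan says.** SAP Section 6.2.1 lists among the adverse event summaries: "Exposure-adjusted incidence rate (EAIR) for TEAEs by SOC and PT". The formula is in SAP Section 8.1. It works treatment by treatment:

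- **Subject with an event.** The rule begins "If a subject has at least 1 treatment emergent event while on a particular treatment", and time runs from the start of that treatment to first onset.
- **Subject without an event.** Time is that treatment's stop date minus its start date, plus "1 + 30 days (if subject discontinued or subject completed but is not rolling into IM011075 study". A subject who completes and rolls over gets plus 1 only. There is no third branch.

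The surrounding text bears on how this should be read:

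- SAP Section 6.3.4.1 defines placebo duration without a tail: "Placebo = Date of last dose of placebo – date of first dose +1".
- SAP Section 8.4 sets "Period 2 = Week 16 visit date +1 to Week 52 visit date", and SAP Section 6.2.1 assigns an event to a period by the first dispensation date in that period.
- SAP Section 4.2 closes the treatment-emergent window 30 days after the final dose of study treatment.
- SAP Section 6.0 and Protocol Section 9.5 show a placebo column for the first 16 weeks. After that, switchers form their own group: "Subjects who switched from placebo to BMS-986165 6 mg QD (including Week 16 through Week 52".
- SAP Section 7.2 provides an unblinded analysis of data up to Week 16, then adds: "All final, planned analyses identified in this statistical analysis plan will be performed only after the last subject has completed the study".

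**The concern.** Exposure is counted per treatment, while the tail depends on a status fixed at the end of the study. Every placebo subject who reaches Week 16 is meant to switch, so the planned path through the placebo arm is the one the rule leaves out.

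Two event-free switchers with identical placebo periods would get different placebo exposure because of a rollover decision about 36 weeks later (52 − 16). The Protocol synopsis expects some completers not to roll over. A switcher who later stops BMS-986165 would also get the tail on placebo, if discontinuation is read at subject level.

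The extra days are on BMS-986165, whose own exposure already starts at the switch. Events on those days belong to Period 2 and do not occur on placebo. The placebo denominator therefore grows with no matching cases, and the rate can only fall. EAIR is meant to compare treatments with unequal follow-up, so counting the same days under both treatments defeats its purpose.

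At the Week 16 lock there is a separate gap. Subjects continuing on treatment, in either arm, have neither discontinued nor completed, so no branch gives their exposure.

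**Working it through.** The documents state no EAIR, exposure total or rollover share, so there is no figure of theirs to reproduce.

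**Inputs**
- Placebo arm: about 219 subjects randomized 2:1 (SAP Sections 2.1 and 2.3), so 219/3 = 73.
- Placebo days: the Week 16 target is Day 113, and the period's last dose date is the last visit date minus 1 (SAP Section 8.1). Day 1 to Day 112 is 112 days.
- Tail: 30 days.
- q: the share of the placebo arm that switches and then falls under the tail rule. It is not in the documents; 10% to 50% is assumed. All 73 are given 112 days, which ignores dropout before Week 16.

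**Per subject.** 112 + 30 = 142 days, an increase of 30/112 = 26.8%. With the ±3-day visit window the increase is 26.1% (30/115) to 27.5% (30/109). All 30 days are BMS-986165 days if the subject stays on it at least that long.

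**Rare event.** Understatement = 1 − 112/(112 + 30q).

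**Event in a proportion p by Day 112, exponential onset assumed.** Rate λ = −ln(1 − p)/112; correct exposure per subject = p/λ; added exposure = 30q(1 − p); understatement = added/(correct + added). For p = 0.20, correct exposure is 100.4 days and added exposure is 24q days.

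**Whole arm.** Correct exposure = 73 × 112/365.25 = 22.4 person-years. Added if all are event-free = 73 × 30q/365.25.

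**Example with 4 cases, mean onset Day 56 assumed.** Correct exposure = 4 × 56 + 69 × 112 = 7,952 days = 21.77 person-years. EAIR = 100 × 365.25 × 4/7,952 = 18.4 per 100 person-years. The literal rule adds 69 × 30q days.

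| q | Rare event, understatement | p = 0.20, understatement | Person-years added (maximum) | Example EAIR |
|---|---|---|---|---|
| 10% | 2.6% | 2.3% | 0.6 | 17.9 |
| 20% | 5.1% | 4.6% | 1.2 | 17.5 |
| 30% | 7.4% | 6.7% | 1.8 | 17.0 |
| 50% | 11.8% | 10.7% | 3.0 | 16.3 |

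The ceiling for a rare event, at q = 100%, is 1 − 112/142 = 21.1%. Understatement reaches 5% when q = (112/0.95 − 112)/30 = 0.196, about 20%.

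**Against sampling noise.** The exact Poisson 95% limits for 4 cases are 1.090 and 10.242. Divided by 21.77 person-years they give 5.0 to 47.0 per 100, far wider than any shift in the example.

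**The case against.** The strongest reply is that no one has promised the output in question. Both documents show placebo only for the first 16 weeks, and the analysis of those weeks is run when rollover is still unknown for continuing subjects. This stands as a condition: the computed bias needs a placebo EAIR produced or rerun at the final lock. It is plausible, since Section 8.1 defines EAIR for each treatment received and Section 7.2 places the final planned analyses after study end, but it is not stated.

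A second reply is that rollover is possible only after 52 weeks, so the tail naturally belongs to the last treatment. SAP Sections 4.2 and 6.3.4.1 support that intent. They do not amend the formula, however, so a programmer who did the sensible thing would be departing from the written rule.

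Third, the direction of bias depends on reading an event on a treatment strictly. The tail given to ordinary early discontinuers makes sense only if events in the tail can count. Applied to switchers, that reading would put BMS-986165 events in the placebo numerator, against the period assignment in Sections 6.2.1 and 8.4. The understatement would then no longer follow, but the rate would still be wrong.

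Finally, q has no source in the documents, so the percentages are illustrative. That stands.

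**Conclusion.** The rule is wrong as written. For placebo ended by the planned switch, it makes exposure depend on a later and unrelated status, and it can add 30 days of another treatment. If a placebo EAIR is produced at the final lock and read literally, a rare-event rate is understated by 2.6% to 11.8% for an assumed q of 10% to 50%. The effect runs against BMS-986165 and is small beside sampling error. The gap at the Week 16 lock needs no assumption about rollover: exposure is undefined there for everyone continuing on treatment.

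The point is minor. It touches one descriptive safety table and leaves crude adverse event counts and percentages, hypothesis tests and efficacy results unchanged.

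**What to change.** In the EAIR entry of SAP Section 8.1:

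1. Add the 30 days only after the last study treatment a subject receives. For switchers, end placebo exposure on the day before the first BMS-986165 dose, with no tail.
2. Apply no tail at the Week 16 lock, or at the end of Period 1, for any subject continuing on treatment.
3. State whether a placebo EAIR is reported at the final lock.

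The cost is a short SAP text change (about two lines) and one condition in the exposure program. No new data are needed.
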